**Table 2-3 Defined Dates**

Region/Country	Start Date	End Date
Italy	23-Feb-2020	End date has not yet been defined
Rest of the World	01-Mar-2020	End date has not yet been defined

Tabulations of adverse events, SAE, and adverse events of special interest broken down by time of onset according to the following intervals will be provided as well:

- Starting within 4 weeks after first administration of study treatment,
- Starting between 4 weeks and 12 weeks after first administration of study treatment,
- Starting more than 12 weeks after first administration of study treatment.

*For the legal requirements of ClinicalTrials.gov and EudraCT, two required tables on treatment emergent adverse events which are not serious adverse events with an incidence greater than or equal to 5% in any treatment group and on treatment emergent serious adverse events and SAE suspected to be related to study treatment will be provided by system organ class and preferred term on the safety set population.*

*If for a same patient, several consecutive AEs (irrespective of study treatment causality, seriousness and severity) occurred with the same SOC and PT:*

- *a single occurrence will be counted if there is  $\leq 1$  day gap between the end date of the preceding AE and the start date of the consecutive AE*
- *more than one occurrence will be counted if there is  $> 1$  day gap between the end date of the preceding AE and the start date of the consecutive AE*

*For occurrence, the presence of at least one SAE / SAE suspected to be related to study treatment / non SAE has to be checked in a block e.g., among AE's in a  $\leq 1$  day gap block, if at least one SAE is occurring, then one occurrence is calculated for that SAE.*

*The number of deaths resulting from SAEs suspected to be related to study treatment and SAEs irrespective of study treatment relationship will be provided by SOC and PT.*

### **Adverse events of special interest / grouping of AEs**

Adverse events of special interest are the risks as described for both tropifexor and CVC (those that appear in tropifexor Development Safety Profiling Plan or CVC Investigator's Brochure, respectively). These will be summarized with absolute and relative frequency overall and by type of risk / AE.

Relative and absolute frequencies of patients with liver and renal events (see protocol Appendix 2 and 3, respectively) will also be provided.

#### **2.8.2 Deaths**

A separate summary and listing will be provided for deaths, if they occur during the course of the study.

### 2.8.3 Laboratory data

The summary of safety laboratory evaluations will be presented for the groups of laboratory tests (e.g., hematology, clinical chemistry). Descriptive summary statistics for the change from baseline to each study visit will be presented. These descriptive summaries will be presented by test group, laboratory test, and treatment group. Change from baseline will only be summarized for patients with both baseline and post baseline values. Shift tables based on the normal laboratory ranges will be provided. For the shift tables, the normal laboratory ranges will be used to evaluate whether a particular laboratory test value was normal, low, or high for each visit value relative to whether or not the baseline value was normal, low, or high. These summaries will be presented by laboratory test category and treatment group.

The number and percentage of patients with new clinically notable laboratory results after baseline will be presented. Clinically notable laboratory results are listed in Section 5.3.1, for those parameters where ranges are available.

Safety laboratory parameters which are at the same time part of the efficacy analyses will be included in the safety tables as well.

### 2.8.4 Other safety data

#### 2.8.4.1 ECG and cardiac imaging data

ECG data will be summarized by treatment and visit (post-baseline ECGs are performed at Week 24 and Week 48).

The Fridericia QT correction formula (QTcF) will be used for clinical decisions and for analyses.

[figure not shown]
Notable QTcF values and changes from baseline will be summarized at Week 24 and Week 48. A notable value is defined as a QTcF interval of greater than 450 ms for both male and female. Those with QTcF interval greater than 500 ms will also be presented. The categories used for the change (increase) in QTcF are:  $\leq 0$  ms,  $> 0$  and  $\leq 30$  ms,  $> 30$  to  $\leq 60$  ms and  $> 60$  ms.

[figure not shown]

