Any unplanned assessments for: Vital signs, ECG, Hepatitis serology, Liver tests, Serum BUN and Creatinine, Coagulation panel, [REDACTED] Clinical chemistry panel, HbA1c, Urinalysis and Serum pregnancy test must be recorded in the unplanned eCRF.

For patients who discontinue study treatment prematurely before the end of the treatment period for any reason other than withdrawal of informed consent, the Week 48, planned End of Treatment (EOT) and Week 52 End of Study (EOS) visits must be performed.

If a patient refuses to return for these assessments or is unable to do so, every effort should be made to contact them, or a knowledgeable informant, by telephone or by sending appropriate correspondence (i.e. certified letter) immediately. At this contact, the safety (e.g. potential occurrence of AEs or SAEs) and the primary reason for the patient's premature withdrawal should be determined. Documentation of attempts to contact the patient should be recorded in the patient source documents.

Refer to Section 5.6 for additional details regarding procedures for patients who discontinue study treatment or prematurely withdraw.

Patients will be contacted for safety evaluations during the 30 days following the last administration of study treatment.

[figure not shown]
Patients who develop medically important laboratory abnormalities or medically important adverse events (AE) that are considered related to study drug will be followed beyond the End of Study visit until these events have resolved or stabilized.

The following will be considered as medically important:

- i. severe AEs,
- ii. serious AEs,
- iii. hepatic and renal AEs,
- iv. elevated liver enzymes (ALT, AST or alkaline phosphatase >2x ULN and >1.5x baseline).

Table 6-1 Assessment schedule

[figure not shown]
Periods	Screening		Treatment Period										Post Treatment Follow Up	Notes
	-10 to -2	-2 ¹ (no later than) ²	BSL	2	4	8	12	16	24	32	40	48 ¹⁶ TD/EOT		
Screening														
Informed consent	X													
Pharmacogenetic informed consent	X													
Inclusion / Exclusion criteria	X	X	X											
Demography	X													
Medical history/ current medical conditions	X													
Protocol solicited medical history	X													
Assessments														
Physical examination ³	S	S	S		S	S	S	S	S	S	S	S	S	
Prior and concomitant medication	X	X	X	X	X	X	X	X	X	X	X	X	X	
Surgical and medical procedures	X	X	X	X	X	X	X	X	X	X	X	X	X	
Alcohol history / compliance with protocol	X	X	X	X	X	X	X	X	X	X	X	X	X	

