
TD: treatment discontinuation; X: assessment to be recorded on clinical database; S: assessment to be recorded on source documentation
 
1: Screening visit 2 should only be conducted if eligibility is confirmed at screening visit 1;
 
2: Screening visit 2 should be done at least two weeks prior baseline visit to allow sufficient time for liver biopsy central reading
 
3: Full physical examination at screening visit 1, baseline, Week 12, 24 and 48
 
4: For any ECGs with safety concerns, one additional ECG must be performed to confirm the safety finding
 
5: Hepatitis B surface antigen (HBsAg), hepatitis B core antibody (HBcAb) positive, Hepatitis C antibody (HCVAb)
 
[REDACTED]
 
7: See assessments in Section 6.5.4.2. At screening visit 1 this also includes ferritin, transferrin saturation, iron, and if not historically available also ANA, ASMA and AMA
 
[REDACTED]
														

[REDACTED]

Periods	Screening		Treatment Period										Post Treatment Follow Up	Notes
	Week	-10 to -2	-2 ¹ (no later than) ²	BSL	2	4	8	12	16	24	32	40	48 ¹⁶ TD/EOT	
[REDACTED]														

12: Only for pre-menopausal women who are not surgically sterile. The urine pregnancy test should be performed every 4 weeks up to the follow up visit including at week 20, 28, 36 and 44 (including during treatment extension due to COVID-19 pandemic and related measures)
 
13: Assessment at EOT not to be done in case of premature treatment discontinuation unless the patient has received at least 8 weeks of study treatment
 
14. Paired liver biopsies (\leq 6 months or at least 2 weeks prior to baseline and at week 48) are required to confirm the diagnosis of NASH (Steatosis, [REDACTED]) and presence of fibrosis. Baseline biopsy slides, prepared from biopsies performed during the screening period or \leq 6 months prior to the screening visit, will be sent to a Central Reader to determine eligibility. Assessment at EOT not to be done in case of premature treatment discontinuation unless the patient has received at least 24 weeks of study treatment
 
15. Full questionnaire AUDIT at screening, short questionnaire at other visits
 
16. For patients who are unable to come to the study site for week 48, End of Treatment (EOT) visit including liver biopsy as scheduled due to COVID-19 pandemic, you may consider to extend the study treatment as indicated in section 5.5.2.
														

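### QTcF outliers are summarised only at Week 24 and Week 48: a prolongation seen only on an unscheduled ECG has no place in the summary, and no patient-level worst-value count is planned

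*SAP*

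**What the plan says.** SAP 2.8.4.1 presents ECG data by treatment and visit, with post-baseline ECGs at Weeks 24 and 48. On outliers it says: "Notable QTcF values and changes from baseline will be summarized at Week 24 and Week 48". Protocol 9.5.2.5 has the same sentence. The SAP continues: "A notable value is defined as a QTcF interval of greater than 450 ms for both male and female", and "Those with QTcF interval greater than 500 ms will also be presented". It then lists four categories of change, the top two being above 30 up to 60 ms and above 60 ms. The sentence on 500 ms and the categories name no visit of their own.

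The protocol provides for ECGs outside these visits. Section 6 opens a list with "Any unplanned assessments for: Vital signs, ECG, Hepatitis serology, Liver tests" and requires such results to be recorded in the unplanned eCRF. Table 6-1, footnote 4, says: "For any ECGs with safety concerns, one additional ECG must be performed to confirm the safety finding". Section 6.5.5 has a clinically significant abnormality, with QTcF above 500 ms among its examples, repeated and both tracings sent to the core laboratory where applicable. It also says that all ECGs are independently reviewed.

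The laboratory rule in SAP 2.8.3 is not tied to visits: "The number and percentage of patients with new clinically notable laboratory results after baseline will be presented".

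**The concern.** QTcF prolongation is an outlier risk. The useful safety summary is how many patients ever passed a threshold, and a table limited to two visits answers a different question. No post-baseline ECG is scheduled before Week 24, so a prolongation in the first months would be seen only on an ECG taken outside the schedule or at a discontinuation visit. An ECG taken for cause is the one most likely to show a prolongation, and an unscheduled one has no stated place in the summary. Protocol Section 6 also allows visits other than Week 48 to be held remotely during the pandemic, and the listed content of a remote visit includes no ECG. A Week 24 ECG made up later would also fall off the visit.

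At stake is whether the report can state, by arm, how many patients exceeded 450 or 500 ms or rose by more than 60 ms at any time on treatment.

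**Working it through.** The documents give no ECG event rate and no figure to reproduce. The check sets the passages side by side and adds simple arithmetic for scale.

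**1. Which post-baseline ECGs have a place in the summary**

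| ECG | Collected? | Place in the QTcF summary |
|---|---|---|
| Week 24, Week 48 | Yes (Table 6-1) | Yes, stated |
| Discontinuation visit (TD) | Yes; Table 6-1 has one column for Week 48, TD and EOT, and Protocol 5.6.2 labels the TD visit EOT | Not stated; nothing excludes it from Week 48 |
| Repeat after a scheduled ECG of concern | Yes (footnote 4; Section 6.5.5) | Not stated; the first tracing is already counted |
| Unscheduled from the outset | Yes, unplanned eCRF (Section 6) | None stated |

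The clear gap is the last row. SAP 2.1 refers to analysis visits, but the readable text has no rule assigning unscheduled or TD ECGs to one.

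**2. By-visit counts are not patient counts**

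Let *a* patients be notable at Week 24 and *b* at Week 48. The number notable at either visit lies between max(*a*, *b*) and *a* + *b*. With *a* = *b* = 2, that is 2 to 4 patients, or 4% to 8% of 50. This holds even if no unscheduled ECG is ever taken. Exclusion criterion 21 removes patients with QTcF above 450 ms at screening, so a later value above 450 ms will generally be new, and patient incidence is the natural summary.

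**3. Weight of one patient**

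1/50 = 2.0 percentage points. With the 193 patients randomised according to Amendment 3, the average arm is 193/4 = 48.25, and 1/48.25 = 2.1 points. If 2 of 50 exceeded 500 ms and one did so only on an unscheduled ECG, the table would show 1/50 = 2% where the patient count is 2/50 = 4%.

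**4. Chance that an arm of 50 shows at least one case (assumed inputs)**

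Let *p* be the true patient incidence and *s* the share of cases visible only on uncounted ECGs. The documents give neither. The chance is 1 − (1 − *p*(1 − *s*))^50.

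| *p* | *s* = 0 | *s* = 25% | *s* = 50% |
|---|---|---|---|
| 2% | 63.6% | 53.0% | 39.5% |
| 5% | 92.3% | 85.2% | 71.8% |
| 10% | 99.5% | 98.0% | 92.3% |

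For example, *p* = 2% and *s* = 50% give 1 − 0.99^50 = 39.5%. The loss is largest for rare outliers. The true *s* may be close to zero.

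**The case against.** The best defence is that naming Weeks 24 and 48 merely lists the scheduled post-baseline ECGs and was not meant to exclude anything. SAP 2.1 says the analysis will use all collected data, and the table shells, which are not available here, may hold a mapping rule. This is fair as to intent. It does not supply a worst-value count, and a programmer following the text would produce two by-visit tables.

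Three stronger readings are tempting, and the documents do not support them.

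- *Early-discontinuation ECGs are lost.* The TD visit shares the Week 48/EOT column and is required unless consent is withdrawn, so its ECG may well be tabulated as Week 48. What is missing is the statement. It matters because Protocol 5.6.2 calls for the TD visit as EOT, while Section 6 calls for the planned Week 48 EOT visit. A patient who stopped early might therefore contribute a tracing from around the stop or one taken long afterwards.
- *A patient above 500 ms who stops drug appears nowhere.* Section 6.5.5 sends clinically significant abnormalities to the medical history or AE pages as appropriate. If recorded as an AE, the finding enters the tables of SAP 2.8.1 whatever the visit. That route depends on investigator judgement and does not replace a threshold count.
- *The table is biased towards zero, most in the arm with most early stops.* A by-visit table does not by itself count absent patients as non-events, and no discontinuation rate is given.

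The laboratory contrast has limits, since laboratory tests are scheduled at more visits than ECGs. ECG is also not among the primary variables in Protocol 9.4.1, and the non-clinical summaries in Protocol 1.1 report no meaningful cardiac ion-channel effect for tropifexor and no significant ECG effect for CVC. These points lower the priority but do not close the gap.

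**Conclusion.** The point holds in a limited form. The planned QTcF summary covers two scheduled visits, so a prolongation seen only on an unscheduled ECG has no stated place in it. The by-visit counts also do not give the number of patients ever affected. The handling of discontinuation ECGs is unstated, which is not the same as their being excluded.

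The size cannot be determined from the documents. One missed patient is about 2 percentage points per arm; every other figure above rests on assumed incidence and assumed shares. The conclusion also assumes that no rule in redacted text or in the table shells already covers this. It is a worthwhile and inexpensive improvement to a secondary safety table, and it does not put the primary analysis in doubt.

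**What to change.** Keep the Week 24 and Week 48 summaries. Add to SAP 2.8.4.1, and align Protocol 9.5.2.5 with it:

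- one patient-level table by arm giving the number and percentage with worst post-baseline QTcF above 450 ms and above 500 ms, and the maximum increase from baseline in the SAP's existing categories;
- all ECGs used (scheduled, TD, unscheduled and repeat) within the treatment-emergent window of SAP 2.8.1;
- a statement that TD ECGs are included, and which visit counts as EOT for a patient who stops early, since the window runs from it;
- the number of ECGs per arm beside the counts.

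Before programming, reconcile the notable threshold: Protocol Appendix 1 uses above 450 ms for males and above 460 ms for females, while the SAP uses above 450 ms for both.

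The cost is one extra table from data already collected. The drawback is that for-cause ECGs give some patients more chances to be counted, which is why the ECG numbers per arm should be shown.

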#### 2.8.4.2 Vital signs

[figure not shown]
Analysis of the vital sign measurements using summary statistics for the change from baseline for each post-baseline visit will be performed. These descriptive summaries will be presented by vital sign parameter and treatment group. [REDACTED]

Change from baseline will only be summarized for patients with both baseline and post-baseline values. Patients with notable vital signs as defined in protocol Appendix 1 will be listed.

[REDACTED]

## **2.14 Interim analysis**

No interim analysis is planned for the study.

[figure not shown]
## **3 Sample size calculation**

The primary objective of the study is to determine if there is a safe combination between one of the chosen doses of tropifexor and 150 mg of cenicriviroc. However, the assessment will be made based on the whole safety profile and not on quantitatively formulated hypotheses for distinct parameters. Therefore, the sample size is based on the feasibility with respect to expected speed of enrollment and duration of the study, not on formal statistical criteria.

### **3.1 Power considerations with given sample size for safety assessment**

[figure not shown]
Events with a true incidence of 30% and above are likely to be observed (almost 100% probability) in a group of 50 patients (size of each treatment group). Events with true incidences below 10% down to 3% are still very likely to be observed, while events are observed with less than 50% probability only if the true incidence is less than about 2.5% ([Figure 3-1](#)). It is noteworthy, however, that a single patient constitutes 2% in a sample of 50.

**Figure 3-1 Binomial probability to observe an event with given sample size**

Probabilities of the incidence being below a certain threshold are plotted in [Figure 3-2](#) for a sample size of 50 patients when the event is observed in 0, 1, 2, ..., 10 patients (assuming a beta distribution with prior shape parameters 0.33, 0.33).

**Figure 3-2 Predictions for probability of event based on observed number occurring in a group of 50 subjects**

For example, if 0 events are observed, the probability (Prob) that the incidence is  $\leq 5\%$  would be 98.7%. If an event is observed in one patient, the probability that the incidence is  $\leq 5\%$  would be 86.6%. Similarly, if an event is observed in 10 patients (one fifth), the probability that the incidence is  $\leq 20\%$  would be approximately 50% (calculated using R function pbeta).

### 3.2 Power considerations with given sample size for efficacy assessment

To evaluate the effectiveness of tropifexor + CVC with respect to the proportion of patients who have at least a one point improvement in fibrosis at Week 48 compared to baseline (i.e, the response rate), one needs to consider the effect size that one is able to detect with respect to both tropifexor and CVC as monotherapy.

- For CVC, based on information from the CENTAUR Phase 2b study, Friedman (2017), it can be assumed that the monotherapy response rate at Week 48 in F2/F3 patients would be approximately 35%
- For tropifexor, a response rate of 42% is assumed (best-case scenario) based on the interpolation of expected Week 72 response rate and assuming linear improvement over time
- For the combined effect of tropifexor + CVC it will be assumed that 75% of the efficacy for CVC will be added to the effect of tropifexor (i.e. a response rate of  $42 + 0.75 \cdot 35 = 69\%$ )

For comparisons between tropifexor + CVC and CVC monotherapy a 2-group continuity corrected  $\chi^2$  test of proportions with type I error rate of 0.10 (2-sided, no adjustment for multiple comparisons), a sample size of 50 per group results in a power of 95% (nQuery Advisor 7.0).

For comparisons between tropifexor + CVC and tropifexor monotherapy a 2-group continuity corrected  $\chi^2$  test of proportions with type I error rate of 0.10 (2-sided, no adjustment for multiple comparisons), a sample size of 50 per group results in a power of 81% (nQuery Advisor 7.0).

Further scenarios assuming different response rates for tropifexor and the magnitude of effect added to tropifexor by CVC are described in [Table 3-1](#).

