9.8.2 Power considerations with given sample size for efficacy assessment

To evaluate the effectiveness of tropifexor + CVC with respect to the proportion of patients who have at least a one point improvement in fibrosis at Week 48 compared to baseline (i.e, the response rate), one needs to consider the effect size that one is able to detect with respect to both tropifexor and CVC as monotherapy.

- For CVC, based on information from the CENTAUR Phase 2b study, [Friedman 2017](#)), it can be assumed that the monotherapy response rate at Week 48 in F2/F3 patients would be approximately 35%
- For tropifexor, a response rate of 42% is assumed (best-case scenario) based on the interpolation of expected Week 72 response rate and assuming linear improvement over time
- For the combined effect of tropifexor + CVC it will be assumed that 75% of the efficacy for CVC will be added to the effect of tropifexor (i.e. a response rate of 69%)

For comparisons between tropifexor + CVC and CVC monotherapy a 2-group continuity corrected χ^2 test of proportions with type error 0.10 (2-sided, no adjustment for multiple comparisons), a sample size of 50 per group results in a power of 95% (nQuery Advisor 7.0).

For comparisons between tropifexor + CVC and tropifexor monotherapy a 2-group continuity corrected χ^2 test of proportions with type error 0.10 (2-sided, no adjustment for multiple comparisons), a sample size of 50 per group results in a power of 81% (nQuery Advisor 7.0).

Further scenarios assuming different response rates for tropifexor and the magnitude of effect added to tropifexor by CVC are described in [Table 9-4](#).

Table 9-4 Power for detecting a treatment difference between tropifexor + CVC and tropifexor and CVC monotherapy

Assumed tropifexor response rate	Assumed response rate of tropifexor + CVC	Power N = 50/arm vs. tropifexor monotherapy	Power N = 50/arm vs. CVC monotherapy
Current target 42% response rate at Week 48 (50% improvement over OCA)	½ effect of CVC added to tropifexor ((60%)	48%	75%
	¾ effect of CVC added to tropifexor (69%)	81%	95%
	Full effect of CVC added to tropifexor (77%)	96%	99%
Response rate between target and OCA at Week 48 (35%)	½ effect of CVC added to tropifexor (53%)	48%	48%
	¾ effect of CVC added to tropifexor (62%)	81%	81%
	Full effect of CVC added to tropifexor (70%)	96%	96%
Worst case: tropifexor same effect as OCA 28% at Week 48	½ effect of CVC added to tropifexor (46%)	50%	23%

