**Table 3-1 Power for detecting a treatment difference between tropifexor + CVC and tropifexor and CVC monotherapy**

Assumed tropifexor response rate	Assumed response rate of tropifexor + CVC	Power N = 50/arm vs. tropifexor monotherapy	Power N = 50/arm vs. CVC monotherapy
Current target 42% response rate at Week 48 (50% improvement over OCA)	½ effect of CVC added to tropifexor ((60%)	48%	75%
	¾ effect of CVC added to tropifexor (69%)	81%	95%
	Full effect of CVC added to tropifexor (77%)	96%	99%
Response rate between target and OCA at Week 48 (35%)	½ effect of CVC added to tropifexor (53%)	48%	48%
	¾ effect of CVC added to tropifexor (62%)	81%	81%
	Full effect of CVC added to tropifexor (70%)	96%	96%
Worst case: tropifexor same effect as OCA 28% at Week 48	½ effect of CVC added to tropifexor (46%)	50%	23%
	¾ effect of CVC added to tropifexor (55%)	82%	56%
	Full effect of CVC added to tropifexor (63%)	96%	81%

\*Power calculated assuming a two-sided Type I error rate of 0.10

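### Three of the nine combination response rates in the power tables, and one separate power cell, do not follow from the plan's own inputs: a minor table correction

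*SAP*

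**What the plan says.** SAP 3.2 and protocol 9.8.2 build the combination response rate for fibrosis improvement from two monotherapy rates. For CVC they take it that "the monotherapy response rate at Week 48 in F2/F3 patients would be approximately 35" percent, citing the CENTAUR study. The tropifexor input is introduced with "For tropifexor, a response rate of 42% is assumed (best-case scenario". To combine them, "it will be assumed that 75% of the efficacy for CVC will be added to the effect of tropifexor". The SAP then writes the sum out, 42 plus 0.75 times 35, and sets it equal to 69%; the protocol gives only the result, "i.e. a response rate of 69" percent.

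Power against tropifexor is stated together with its method, a continuity-corrected two-group chi-square. The SAP's words are: "type I error rate of 0.10 (2-sided, no adjustment for multiple comparisons), a sample size of 50 per group results in a power of 81" percent. The same wording gives 95% against CVC.

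SAP Table 3-1 and protocol Table 9-4 repeat the construction for tropifexor rates of 42%, 35% and 28%, adding one half, three quarters or all of the CVC rate. That makes nine combination rates and eighteen powers. The three-quarter rows show 69%, 62% and 55% (for example the label starting "¾ effect of CVC added to tropifexor (62"). The last row, whose label starts "Full effect of CVC added to tropifexor (63", shows 81% power against CVC.

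**The concern.** The sum printed in the SAP is not correct as arithmetic, and the same upward step appears in all three rows of that type, including the row that supplies the two powers quoted in the text. The printed powers were calculated at these raised rates, so they are slightly too favourable for the inputs given.

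The second problem is visible without calculation. In the CVC column, 62% vs 35% and 63% vs 35% both carry 81%. Comparator, sample size and significance level are the same, so the larger difference should show the higher power; one of the two cells must be wrong unless the step happens to be lost in rounding, which the check below rules out.

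These are the only power figures given for the efficacy comparisons. Left alone, the false sum and the wrong cell may be carried into the study report.

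**Working it through.** **Inputs** (SAP 3.2 and Table 3-1; same values in protocol 9.8.2 and Table 9-4): CVC 35%; tropifexor 42%, 35% or 28%; shares of the CVC rate 1/2, 3/4 and 1; n = 50 per arm; two-sided significance level 0.10; continuity-corrected chi-square.

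**Step 1: the rates.** Three quarters of 35 is 26.25.

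| Tropifexor | + 1/2 of 35 (printed) | + 3/4 of 35 (printed) | + 35 (printed) |
|---|---|---|---|
| 42 | 59.5 (60) | 68.25 (69) | 77 (77) |
| 35 | 52.5 (53) | 61.25 (62) | 70 (70) |
| 28 | 45.5 (46) | 54.25 (55) | 63 (63) |

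The half-effect rates round half-up to the printed values and the full-effect rates are exact. Only the three three-quarter rates fail, each by 0.75 points upward.

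**Step 2: reproduce the plan's power.** With d = p2 − p1, p̄ the mean of the two rates and q = 1 − p,

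power = Φ{ [(d − 1/n)√n − 1.645 √(2 p̄ q̄)] / √(p1q1 + p2q2) }.

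For 69% vs 42%: (0.27 − 0.02) × 7.071 = 1.768; 1.645 × √(2 × 0.555 × 0.445) = 1.156; √(0.2436 + 0.2139) = 0.676. Then (1.768 − 1.156)/0.676 = 0.904, and power is 81.7% (printed 81%). Applied to all eighteen cells at the printed rates, the formula gives the printed figure in seventeen, once the decimals are cut off rather than rounded.

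**Step 3: power at the rates the inputs give.** For 68.25% vs 42%: (0.2625 − 0.02) × 7.071 = 1.715; 1.645 × √(2 × 0.55125 × 0.44875) = 1.157; √(0.2436 + 0.2167) = 0.678. Then (1.715 − 1.157)/0.678 = 0.822, and power is 79.4%. The affected cells are:

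| Comparison, unrounded rate | Printed power | At printed rate | At unrounded rate |
|---|---|---|---|
| 68.25 vs 42 | 81 | 81.7 | 79.4 |
| 68.25 vs 35 | 95 | 95.1 | 94.2 |
| 61.25 vs 35 (both columns) | 81 | 81.3 | 79.1 |
| 54.25 vs 28 | 82 | 82.3 | 80.2 |
| 54.25 vs 35 | 56 | 56.7 | 53.7 |

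For scale, ordinary rounding elsewhere in the table has a similar effect: 59.5% vs 42% gives 46.2% against the printed 48%.

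**Step 4: the cell that does not reproduce.** For 63% vs 35%: (0.28 − 0.02) × 7.071 = 1.838; 1.645 × √(2 × 0.49 × 0.51) = 1.163; √(0.2275 + 0.2331) = 0.679. Then (1.838 − 1.163)/0.679 = 0.995, and power is 84.0%, printed 81%. The formula gives 81.3% for 62% vs 35%, so the printed 81% is the value for the rate one point lower. Exact enumeration of the corrected test gives 82.7% for 63% and 79.9% for 62%; it does not make the two cells equal either.

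**Step 5: the planned test.** Without the continuity term, 68.25% vs 42% gives 0.2625 × 7.071 = 1.856, (1.856 − 1.157)/0.678 = 1.03, and power 84.9%.

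**The case against.** The CVC rate is given only as approximate. If an unrounded rate c was used, 28 + 0.75c must reach 54.5 and 28 + c must stay below 63.5, so c lies between about 35.34% and 35.49%. Any such value yields all nine printed rates by ordinary rounding, and power against tropifexor at 42% would then be 80.2% to 80.6%. This stands as a possible explanation of the rates. But neither document states such a value, and the SAP puts 35 into the written sum. It also leaves the 63% vs 35% cell unexplained.

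A reader might infer that the trial is underpowered because the comparison with tropifexor falls below 80%. The documents do not support that. The 81% is right for the printed 69%; the drop is a rounding effect on an assumed rate. No power target is stated, the sample size is justified by feasibility (protocol 9.8, SAP 3), and no hypotheses are pre-specified. The 42% tropifexor rate is labelled a best case, and the tables already run from 23% to 99%. Nor does the wrong cell add to that inference: it belongs to the 28% scenario and errs in the other direction.

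A reader might also infer that the powers describe the wrong test, since the planned analysis is a Cochran-Mantel-Haenszel (CMH) test stratified by baseline fibrosis stage. The documents name the power test openly as a continuity-corrected chi-square. They do not say whether the CMH test carries a correction. If it does not, the printed figures may be conservative for it.

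Finally, enrolment had closed with 193 randomized by protocol Amendment 3, so the tables no longer inform a design choice. That limits the importance of the errors but does not make the figures right.

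**Conclusion.** The point holds as a minor table correction. At the stated inputs, three of nine combination rates are 0.75 points too high. The powers in those rows are then overstated by about 2 to 3 points in most cells, and by about 1 point for 68.25% vs 35%. One further cell, 63% vs 35%, understates power by 3 points (81% for 84%).

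The rate finding takes the CVC rate as exactly 35%, as the SAP's own sum does; a rate near 35.4% would remove it. The cell finding rests on the formula that reproduces the other seventeen cells, and on the fact that two different rates against one comparator carry the same power. Neither finding changes the sample size, the analysis or any decision rule.

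**What to change.** In SAP 3.2 and Table 3-1, and in protocol 9.8.2 and Table 9-4:

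- Either print the three-quarter-effect rates as 68%, 61% and 54%, or as 68.25%, 61.25% and 54.25%, with power to match, and correct the sum written in the SAP; or state the unrounded CVC rate that was used. At the unrounded rates the powers are those in the last column of the Step 3 table. At the whole percents they are 78.7% (68 vs 42), 93.9% (68 vs 35), 78.4% (61 vs 35), 79.5% (54 vs 28) and 52.7% (54 vs 35).
- Change the 63% vs 35% cell from 81% to 84%.
- Optionally, add a note that the figures are for a continuity-corrected chi-square and not the planned CMH test, and may be conservative for it if that test is run without a correction (about 85% for an uncorrected chi-square at 68.25% vs 42%).

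The cost is a small edit to one section and one table in each document. The power quoted against tropifexor becomes slightly less favourable. Nothing changes for patients, the sample size or the analysis.
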